The initial treatment of Patients with Functional constipation is based on fiber. There are multiple fiber products in the market, which are Promoted as a supplement for constipation without any scientific evidence to support ITS use. Furthermore, the tolerability of These compounds limits long-term Their use in esta patient population. Scientific evidence is required to support the effectiveness in the use of These fiber supplements in Patients With functional constipation.

6. Justification

There are multiple fibers are in the market That Promoted as a beneficial supplement for Patients With constipation, DESPITE esta, there is not enough scientific evidence derived from randomized and controlled studies to support ITS use. THEREFORE, it is Necessary to Provide evidence to support the use of blue agave fructans Tequilana Weber in Patients With functional constipation.

7A. hypothesis

Defined as a verifiable statement About the relationship Between a variable-dependent and an independent variable. (Remember That the concepts of "null hypothesis", "alternate hypothesis" are related to the statistical analysis So They Should not be included in this item)

General Hypothesis:

Plantago Psyllium When Compared With, the blue agave fructans Weber Tequilana have a like effect or are more effective in Improving functional constipation in adult patients.

Objectives

PRIMARY

1. To Evaluate the efficacy of the blue agave fructans Tequilana Weber in Patients With functional constipation.

SECONDARY

1. To compare the efficacy and tolerability of 5 and 10g doses of blue agave fructans Tequilana Weber in Patients With functional constipation.
2. To Evaluate the impact of the consumption of blue agave fructans Tequilana Weber on the quality of life of the subjects WHO ingest it by Applying the quality of life questionnaire SF-36.
3. To determine the impact of the blue agave fructans of Weber Tequilana intake in the fasting glucose, glycosylated hemoglobin A1c and the lipid profile (metabolic profile) of the subjects WHO ingest it.
4. To Evaluate the presence of short chain fatty acids (butyrate) before vs after the treatment with blue agave fructans Tequilana Weber.
5. To determine the impact of the ingestion of blue agave fructans Tequilana Weber in the microbiota before vs after ingestion.
6. Evaluate to the tolerance to the ingestion of blue agave fructans Weber Tequilana through the use of breath test.

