The study to be Carried out will be Explained and read and, where appropriate, the informed consent will be signed by the Patient During the initial visit (Visit 1) of eligibility, Where the subject will be Given 2 questionnaires (see annexes), one They meet to determine if the ROME III criteria for functional constipation (FC) and another to ASSESS if the patient does not meet the criteria for irritable ROME III bowel syndrome (IBS) and a baseline breath test will be performed.

Having met the inclusion criteria, the patient will be EVALUATED by a graduate in nutrition with the objective of Evaluating the fiber intake in the subject's usual diet. The amount of daily fiber intake will be standardized and a diary will be Given to Evaluate Said intake (see annexes) as well as a diary Where the subject will keep a record of his / her evacuations (see annexes).

In Addition, the previous use of fiber supplements and laxatives, which must be suspended at Least 2 months prior to randomization, will be EVALUATED.

The subject will return to a second visit (Visit 2) (Which will depend on Whether the patient is taking laxatives or fiber supplements) for a complete physical evaluation and the fiber intake diary will be Assessed to determine the amount of fiber intake in the diet as well as the diary of evacuations and the SmartPill © will be Given and That way, the patient will return to the hospital to register the data after the capsule Having evacuated.

The patient will return a week later (Visit 3) on a 12 hour fast, the fiber intake and the evacuation diaries will be re-EVALUATED and will be EVALUATED They again by a nutritionist. A new breath test will be Carried out. The subject will be

Asked to complete the SF-36 Quality of Life Questionnaire. A stool sample will be Collected for ITS analysis in Addition to a blood sample for determination of fasting glucose, glycosylated hemoglobin A1c, Insulin and full lipid profile.

The subjects will be randomized to receive one of four treatments That can be Psyllium plantago 15g, blue agave Tequilana Weber fructans at doses of 5, 10g and blue agave Tequilana Weber fructans at a dose of 5 g + 10 g excipient for a concentration of 33 % of blue agave fructans Tequilana Weber.

The randomization will be computer-generated with a participation number and the assignment of the treatment will be consecutive.

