The product will be supplied in identical bottles With the same amount of powder in a container That will only be identifiable With the name of the protocol as well as the patient's number.

The patient will be provided with a measuring spoon to administer the amount of product Necessary for each of the doses (5, 10 and 15g respectively) or with envelopes Containing the exact Amounts Weighed.

The patient will be instructed to keep a diary of the diet, of the evacuations and a sheet to ASSESS adverse effects. The subject will return (Visit 4) at the end of a month \pm 5 days on a 12 hour fast and Their adherence will be Assessed by product weight in the container subtracting the number of grams required daily ACCORDING TO the assignment of treatment.

The fiber intake diaries will be EVALUATED again by the nutritionist, the evacuation will Also be EVALUATED diary. A medical evaluation will be Carried out That includes questioning and physical evaluation. Subsequently, a blood sample will be to determine fasting glucose Obtained, glycosylated hemoglobin A1c, insulin and lipid profile and a full sample of excrement will be Obtained and SmartPill® will be Given.

The patient will Continue with the supplement in the same container and will be scheduled for a month later. In the end-of-treatment visit visit (visit 5), the fiber will be EVALUATED journals consumption again by a nutritionist and the evacuation will be EVALUATED diary as well.

A medical evaluation will be Carried out That includes questioning and physical evaluation and Their adherence will be Assessed by weighing the product in the container, subtracting the number of grams That it requires daily ACCORDING to the treatment assignment or delivery by the patient of the empty envelopes used.

Subsequently, a blood sample will be to determine fasting glucose Obtained, glycosylated hemoglobin A1c, insulin and lipid profile and a full sample will be Collected stool and breath test at the end will be Carried out.

For end of the visit, Which Will Be Carried out one month after stopping the treatment, the evacuation will be EVALUATED diary and a stool sample will be Collected and with it the intervention in the part of the study will end. Total The follow-up duration for each patient will be 3 months, enough time to observe and compare the effect of the fibers to be used. It is Important to mention That in recent studies Carried out by the same team and with blue agave Tequilana Weber fructans,

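### No record of gas or bloating before treatment is described, so the adverse-effect sheet cannot separate symptoms already present from those that arise on treatment

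*Combined protocol and SAP*

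**What the plan says.** Secondary objective 1 (Objectives, after Section 7A) is "To compare the efficacy and tolerability of 5 and 10g doses of blue agave fructans Tequilana Weber". Secondary objective 6 is separate: "Evaluate to the tolerance to the ingestion of blue agave fructans Weber Tequilana through the use of breath test".

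In Section 8 (General Design), Visit 1 issues two diaries: "a diary will be Given to Evaluate Said intake (see annexes) as well as a diary Where the subject will keep a record of" evacuations. Visit 2 looks at the same two. At Visit 3, just before randomisation, "the fiber intake and the evacuation diaries will be re-EVALUATED". The adverse-effect sheet is first mentioned after the randomisation and product-supply paragraphs: "The patient will be instructed to keep a diary of the diet, of the evacuations and a sheet to ASSESS adverse effects".

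The breath test is different. At Visit 1 "a baseline breath test will be performed", and the narrative repeats it at Visit 3 and at Visit 5.

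Section 12 expects flatulence and bloating from fructans and says that side effects and use of rescue therapy will be recorded. It gives no rule for complaints present before the first dose. The statistical analysis plan foresees paired comparisons with baseline within groups, and ANCOVA with covariates that it does not name.

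**The concern.** Flatulence and distension are the complaints the plan expects from the product, and patients with constipation may have them already. The Rome III list printed in Section 8 requires absence of abdominal pain or discomfort, and Section 9 excludes abdominal pain as an alarm feature. Neither lists gas or distension.

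With no reading before treatment and no fibre-free arm, a patient who was bloated throughout the run-in and a patient who became bloated on product can look the same on the sheet. What is at stake is how far the reported intolerance rate can be trusted, and how well a difference between 5 g and 10 g can be seen with 15 patients per arm. The Problem definition section names tolerability as what limits long-term use of these products. A baseline cannot be collected once dosing has begun.

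**Working it through.** The plan states no figure for tolerability, so there is none to reproduce. The check is a comparison of passages followed by illustrations.

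**1. What is recorded before treatment (Section 8)**

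| Visit | Named in the narrative | Gas or bloating record? |
|---|---|---|
| 1 | Rome III and IBS questionnaires, breath test, fibre diary, evacuation diary | none described |
| 2 | physical evaluation, both diaries, SmartPill | none described |
| 3 | both diaries, breath test, SF-36, stool and blood samples | none described |
| Dispensing | diet diary, evacuation diary, adverse-effect sheet | first appearance |

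**2. Is there another reference for background symptoms?** The arms are agave fructans 5 g, 10 g, 5 g plus 10 g excipient, and psyllium 15 g. All are active fibre, so none supplies a background rate. In the crossover tolerance study of oligofructose and inulin cited in the Background, the control symptom score was 2 against 2.5 to 3.6 on active product. So 2/3.6 = 56% to 2/2.5 = 80% of the active-product score was also seen on control. That study's questionnaires began at hour 0. The other cited inulin tolerance study opened with a placebo period.

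**3. Dilution of a yes/no outcome.** Inputs: n = 15 per arm (Section 8); two-sided alpha 0.05 (the plan gives 0.05 without sidedness). Assumed: product causes symptoms in 20% versus 50% of patients who were symptom-free, and a share b of patients had symptoms beforehand.

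Observed rate = b + (1 − b)q, where q is 0.20 or 0.50, so the observable difference is (1 − b) × 0.30. Power is from the normal approximation with pooled variance under the null.

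| b | Rates | Difference | Power |
|---|---|---|---|
| 0% | 20% v 50% | 30 points | 40% |
| 20% | 36% v 60% | 24 points | 25% |
| 40% | 52% v 70% | 18 points | 17% |
| 60% | 68% v 80% | 12 points | 11% |

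The rates in both arms rise with b while the difference shrinks.

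**4. Chance imbalance.** With two independent binomial counts of 15, the probability that the arms differ by 3 or more patients with symptoms at baseline is 25% for b = 20% and 35% for b = 40% or 60%.

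**5. Gain from a baseline score.** This applies only if the sheet yields a roughly continuous score. With correlation r between baseline and on-treatment score (assumed), the variance left after adjustment is 1 − r², and the equivalent sample size is n/(1 − r²). The detectable difference at 80% power is (1.960 + 0.842) × √(2/15) × √(1 − r²) SD.

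| r | Variance removed | 15 per arm worth | 12 per arm worth | Detectable difference, n = 15 |
|---|---|---|---|---|
| 0 | 0% | 15 | 12 | 1.02 SD |
| 0.5 | 25% | 15/0.75 = 20 | 12/0.75 = 16 | 0.89 SD |
| 0.7 | 49% | 15/0.51 = 29 | 12/0.51 = 24 | 0.73 SD |

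The 12 is 15 × 0.8, using the 20% loss in the sample-size section.

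**The case against.** Several points on the other side are sound.

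- A reader might infer that symptoms already present will be counted as intolerance. The plan does not say so; it has no counting rule. Visits 4 and 5 include a medical evaluation with questioning, at which onset could be asked. What stands is that the sheet itself gives no means of separation, and recall at a month is a weak substitute for a prospective record.
- A reader might infer that tolerability cannot be adjusted for baseline at all. That is too broad. Objective 6 uses the breath test, which has values before treatment. Exhaled gas is not a symptom score, however, so it does not fill the gap for objective 1.
- A reader might infer that the dose comparison is biased. It is not: background symptoms are balanced in expectation by randomisation. The loss is dilution, precision and exposure to chance imbalance.
- Entry conditions limit baseline symptoms in part: no pain or discomfort, no IBS, no fibre supplements for 2 months, dietary fibre standardised. They do not address gas and distension directly.
- The questionnaires and diaries are in annexes that are not in the text, so a bloating or gas item used before treatment cannot be excluded. This limit is real.
- The comparison is weak anyway: 40% power in the illustration even with no background symptoms. Section 10 also lists no tolerability variable, so moving an undefined sheet earlier is not enough. This stands, and the fix therefore includes a definition.

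**Conclusion.** The point holds in a limited form. As described, symptom tolerability under objective 1 has no like-for-like baseline and no fibre-free comparator. Absolute intolerance rates in each arm could be inflated. The contrasts of 5 g with 10 g, and of agave with psyllium, lose contrast and precision and are exposed to chance imbalance, without systematic bias.

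The size is illustrative only. The documents give neither the prevalence of gas or bloating at entry nor its correlation with later symptoms. Under the assumed correlations, leaving out the baseline forgoes a gain equivalent to about 5 to 14 extra patients per arm on 15, or about 4 to 12 on 12 completers. If the sheet only lists events, those equivalents do not apply, and the dilution table is the relevant guide. The conclusion also depends on the annexed forms holding no symptom item for use before treatment, which the sponsor can confirm. The matter concerns a secondary objective, but the remedy is cheap and has to be in place before dosing.

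**What to change.** - Hand out the existing adverse-effect sheet at Visit 1, together with the evacuation diary.
- Take the week before Visit 2 as the symptom baseline. The week between Visits 2 and 3 follows the first SmartPill, which could disturb gas and bloating. The interval from Visit 1 to Visit 2 is not fixed in the text, so state that it must allow at least one full week of recording.
- Define symptom tolerability as new or worsened symptoms against that week, and list it among the secondary variables in Section 10.
- In the statistical analysis plan, name the baseline symptom score as covariate in the tolerability comparisons. If the sheet only lists events, use presence at baseline instead.
- If an annexed form already records gas or bloating before treatment, say so and state how it will be used.

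The cost is slightly more patient recording in the run-in. The form already exists, no visit is added, and treatment is unchanged.

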effects on intestinal transit Have Been observed from the first week of intake, in fact this is one of the Reasons to focus the study on functional constipation and intestinal transit.

Breath test:

A breath test will be Carried out in order to measure hydrogen and methane Concentrations previousle Exhaled In Patients randomized in visits 1 and 5.

In order to carry out the breath test gas chromatography equipment will be used, brand Quintron Breath Tracker.

For That, The Patients will be Asked:

- Not to take antibiotics prior weeks At least to the test.
- Stop the intake of food rich in fibers and starches 24 h before the test.
- Not to take alcohol, or smoke
- Have a minimum of 8 hours fasting
- Perform oral hygiene before starting the test and during the performance of measurements.

This test lasts 3 hours, during which the patient can not leave the laboratory facilities motility, can not speak too much or sleep. Exhaled air samples are taken every 15 minutes during this period.

SmartPill®:

[figure not shown]
SmartPill® test will be conducted on visits 2 and 4.

colonoscopy:

Colonoscopy study is a tool which will be subject to scrutiny patients ≥ 55 years with newly diagnosed constipation or those where changes in bowel habits observed in this age group. This fundamental objective, rule out potentially serious diseases and not to delay the diagnosis of these during the research study. one colonoscopic study all patients who have constipation and any of the following characteristics will be used:

1. Diagnosis of constipation less than 1 year
2. Subjects ≥ 55 years who do not have colonoscopic evaluation in the last 3 years prior to study entry
3. Chronic but with alarm data (: Unexplained weight loss, recent transrectal bleeding < 6 months, recent changes in the defecation pattern example) Constipation

Study Flow Chart

Patients include:

Studies with fiber supplements (Psyllium, Plums⁸) Have included 25 to 30 patients per group to find differences between groups.

In total it is planned to include 60 patients randomized as follows: 15 patients receive fructans blue agave Tequilana Weber dose of 5 g, 15 patients received the dose of 10 g, 15 patients received the dose of 5g of agave fructans blue Tequilana Weber + 10 g excipient and 15 patients received 15 g plantago psyllium.

9. Methodology Selection Criteria

a) Inclusion criteria (consider not participating in other research and contraception if necessary)

- Patients over 18 years old.

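### The breath-test schedule contradicts itself, and the only test labelled baseline precedes fibre standardisation and any washout, so the within-arm change for secondary objective 6 is not clearly a treatment effect

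*Combined protocol and SAP*

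**What the plan says.** All of this is in section 8 (Methodology: General Design) of the combined protocol and SAP unless another section is named.

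- **Visit 1 (eligibility).** Questionnaires are given "and a baseline breath test will be performed".
- **After eligibility is met.** "The amount of daily fiber intake will be standardized", and diaries are issued. Earlier fibre supplements and laxatives are reviewed, "which must be suspended at Least 2 months prior to randomization".
- **Visit 2.** Its timing is conditional: "Which will depend on Whether the patient is taking laxatives or fiber supplements".
- **Visit 3, a week after Visit 2.** "A new breath test will be Carried out". The SF-36, stool sample and blood sample are taken here, and randomisation is described next.
- **Visit 5 (end of treatment).** A "breath test at the end will be Carried out".
- **Breath test paragraph.** The test is placed "In Patients randomized in visits 1 and 5". Visit 3 is not mentioned.

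Secondary objective 6 is to evaluate tolerance of the agave fructans by breath test. It names no baseline visit. The secondary variables I to V in section 10 do not include breath gases. The statistical analysis plan under Data analysis has paired comparisons of basal with later values within groups, and percentage change between groups, but does not say which visit is basal.

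**The concern.** The two descriptions cannot both be followed. A site working from the Breath test paragraph would omit the Visit 3 test. That is the only test taken after fibre standardisation and any washout but before the first dose, and it could not be recovered later. An analyst with all three results would still find only one labelled baseline, the one at Visit 1.

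A before-after change that starts at Visit 1 includes whatever happens to breath hydrogen and methane when dietary fibre is standardised and when supplements or laxatives are stopped. No arm is free of fibre: three receive agave fructans and one receives psyllium. The trial therefore has no untreated comparison that would separate these changes from the effect of the fructans, and the within-arm change carries more weight for this objective than it would in a placebo-controlled design.

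**Working it through.** The plan states no figure on this point, so there is nothing to reproduce. The check compares the schedules, works out the intervals and decomposes the change.

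**1. Schedules side by side**

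| Source in section 8 | Visit 1 | Visit 3 | Visit 5 | Tests before treatment |
|---|---|---|---|---|
| Visit descriptions | yes | yes | yes | 2 |
| Breath test paragraph | yes | not named | yes | 1 |

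As a cross-check, the SmartPill line just below puts that test at Visits 2 and 4, which agrees with the visit descriptions. The disagreement is confined to the breath test.

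**2. Order of events.** Visit 1 test; then fibre standardisation and, where needed, suspension of supplements and laxatives; then Visit 2, timed by that need; then Visit 3 with its test and the other pre-treatment measures; then treatment; then the Visit 5 test.

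**3. Intervals.** Inputs: suspension of at least 2 months before randomisation, and about 2 months of treatment (Visit 4 at one month, Visit 5 a month later). Assumption: a patient who needs washout stops at or after Visit 1.

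- Visit 1 to Visit 5: at least 2 + 2 = 4 months, of which at least 2 precede treatment. At the minimum, 2/4 = 50% of the interval is before the first dose.
- Visit 3 to Visit 5: about 2 months, all on treatment.

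**4. Decomposition of the mean within-arm change.** Let p be the share of patients needing washout, W the mean effect of washout on breath gas in those patients, S the mean effect of standardising dietary fibre, and T the mean change over the treatment period.

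- Visit 5 minus Visit 1 = p × W + S + T
- Visit 5 minus Visit 3 = T

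T still contains any drift during treatment, because no arm is untreated. The documents give none of p, W or S. Over the whole possible range of p, the washout term is:

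| p | 0 | 0.25 | 0.50 | 0.75 | 1 |
|---|---|---|---|---|---|
| p × W | 0 | 0.25 W | 0.50 W | 0.75 W | W |

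S applies to every patient, whatever p is.

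**5. Between arms.** Both extra terms arise before randomisation, so in this additive model they cancel in expectation between arms. What remains is chance imbalance. With 15 patients per arm, the SD of the difference in the share needing washout is √(2p(1−p)/15):

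- p = 0.25 or 0.75: √(2 × 0.1875/15) = 0.158
- p = 0.50: √(2 × 0.25/15) = 0.183
- p = 0 or 1: 0

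That adds noise of about 0.16 W to 0.18 W to a between-arm difference for p from 0.25 to 0.75, with no systematic shift.

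**The case against.** Six points can be made on the other side.

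- **The washout group may be empty for fibre.** Section 9 excludes patients who took fibre supplements in the last 2 months. If that is judged at Visit 1, nobody enrolled needs a fibre washout. This stands as a limit on size. But the criterion gives no reference date, section 8 expressly provides for patients taking supplements or laxatives at that stage, and the laxative exclusion covers only chronic use of stimulants. Fibre standardisation affects everyone in any case.
- **Test preparation controls recent diet.** The Breath test paragraph asks patients to stop foods rich in fibre and starch for 24 hours and to fast for at least 8. This partly standardises recent intake. It may not remove longer-term effects: the theoretical framework itself says that regular intake can increase the capacity of the microbiota to ferment.
- **The estimand is inferred.** Objective 6 has no before-after wording, although objectives 4, 5 and 7 do, and no analysis of Visit 5 against Visit 1 is written down. True. The conclusion is therefore conditional on Visit 1 being used. The missing definition is part of the problem.
- **The sentence is garbled.** It does not say that these are the only visits, and it attaches randomisation to Visit 1. The flow chart is not readable in the copy reviewed and may list the tests. These are reasons to reconcile the text rather than to assume which description governs.
- **A reader might infer that the agave effect is understated.** The background reports that 5 g and 7.5 g of agave inulin raised breath hydrogen, so earlier fibre might raise the Visit 1 value and shrink the measured rise. The documents do not support this as a finding. Those were healthy subjects on agave inulin. The supplements these patients took before are unknown, psyllium is described as only moderately fermentable, and no sign is given for stopping laxatives or standardising diet.
- **A reader might also infer that the arm comparisons are biased.** They are not, because the extra changes precede randomisation.

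**Conclusion.** The point holds as an internal inconsistency with a consequence for one secondary objective. The visit descriptions give three breath tests, the Breath test paragraph names two, and the only test labelled baseline is the one taken before fibre standardisation and any washout. If that test serves as baseline, the within-arm change in hydrogen and methane cannot be attributed to treatment alone. The timing is clear: on the minimum schedule, half of the Visit 1 to Visit 5 interval is off treatment for a patient needing washout.

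Neither the size nor the direction of the effect on breath gas can be stated. Both depend on p, W and S, which are not given, and p could be near zero for fibre supplements. No percentage attenuation and no bias towards zero should be claimed. Randomised contrasts lose some precision but are not systematically shifted. The primary outcome is not affected. If Visit 3 is used as baseline, the washout and standardisation terms drop out.

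**What to change.** 1. Make the visit descriptions and the Breath test paragraph in section 8 list the same visits: 1, 3 and 5. Check the flow chart against them.
2. State in section 10 and under Data analysis that the baseline for objective 6 is the Visit 3 test, done before the first dose, and that within-arm change is Visit 5 minus Visit 3. Use the same baseline for any percentage change or ANCOVA adjustment.
3. Remove the baseline label from the Visit 1 test and describe it as a screening value.
4. Reconcile the reference date of the section 9 fibre-supplement exclusion with the suspension rule in section 8, and record which patients needed a washout so that the share can be reported.

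The cost is protocol and SAP wording plus one recorded item. The Visit 3 test is already in the visit descriptions, so no procedure is added to them. A site that had planned only Visits 1 and 5 would need one further test per patient.
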